4.0 OBJECTIVE(S) & HYPOTHESIS

Our overall goal is to determine which commonly used LA or combination of LA demonstrates the most ideal properties in a patient receiving an epidural for labor pains. As anesthesiologists, we strive to provide a fast-acting and safe anesthetic in these patients to elicit rapid pain relief in laboring mothers.

Currently, there are several ways in which we activate a labor epidural with LA. Three of the more common LA solutions used are 1% lidocaine, 0.125% bupivacaine, or a combination of bupivacaine and lidocaine. In a prospective, randomized, double-blinded study, we plan to determine if one solution is more superior to the others.

Briefly, after consent is obtained, a standard anesthesia provider will place a labor epidural in regular fashion. After a negative test dose, the anesthesia provider will then administer the study solution the patient was randomized to receive (10 mL of 0.125% bupivacaine, 10 mL of 1% lidocaine, or 5 mL of 0.125% bupivacaine plus 5 mL of 1% lidocaine). The standard epidural infusion bag will then be started by the anesthesia provider. Both the patient and investigator will be blinded to the study. Once the study drug bolus has been given, the investigator will collect the data.

Data to be collected will be: sensory level (by pin prick and ice), degree of motor block by using a modification of Bromage's scale³ (see section 8.0), maternal heart rate (HR) and blood pressure (BP), the need to administer a vasopressor agent (phenylephrine or ephedrine) to treat hypotension, the amount of vasopressor given, and fetal heart rate (FHR). Starting with the initial bolus (Time 0 or T₀), data will then be collected 5, 10, 15, and 20 minutes after the bolus.

The primary outcome for this study is the time it takes to achieve a T₁₀ dermatome level by pinprick (which signifies an adequate epidural level for labor analgesia).

Secondary outcomes include: the total spread (both cephalad and caudal) of the LA (dermatome level to be determined by pin prick and ice), degree of motor block, incidence of maternal hypotension defined as a BP >20% decline from baseline, the need to administer a vasopressor to treat the hypotension, the amount given, and if there is any change in fetal status by monitoring FHR.

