Pregnant patients who are admitted to the L&D floor at the WIC and have none of the above mentioned exclusion criteria will be approached about enrolling in the study. Informed consent will be obtained before any obstetric intervention occurs that might cause pain or altered mental status to the patient. Once the patient requests for her epidural to be placed, the investigator will be notified. Any qualified anesthesia provider will then place the labor epidural. Per our routine practice, the epidural will be placed in the L₂₋₃ or L₃₋₄ interspace, secured at plus 5 cm from the loss of resistance distance at the skin, and the routine test dose of 3 mL of 1.5% lidocaine with 1:200,000 epinephrine will be administered to rule out spinal or intravascular placement of the epidural catheter. After the epidural catheter is deemed safe to use (from a negative test dose), the anesthesia provider will administer the LA solution the patient has been randomized to receive: 10 mL (B), 10 mL (L), or 10 mL (BL), and the standard LA infusion will be connected to the epidural and started. The time that the LA bolus occurred will be marked as T₀. The patient's BP, HR, anesthetic level to pin prick and ice, degree of motor blockade, and FHR will be recorded at that time by the blinded investigator. Motor blockade will be tested by a modification of Bromage's scale where: 0 = the ability to maintain a leg lift for prolonged periods; 1 = the ability to lift legs briefly; 2 = the ability to bend knees; 3 = the ability to wiggle toes; 4 = no movement in lower extremities.³ Then at intervals of 5, 10, 15, and 20 minutes, the investigator will document the above mentioned data with the addition of any vasopressor (phenylephrine or ephedrine) required to treat maternal hypotension and the dose.

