If, on administration of the test dose, the epidural catheter is believed to be intravascular (increase in HR > 20% above baseline) or spinal (an acute anesthetic level is noted by hip flexor weakness), then the catheter will be deemed not safe to use, and the patient will be removed from the study. The epidural catheter can be replaced by the anesthesia provider; however, since the data will be flawed from the initial positive test dose, the patient will not be allowed to participate in the study at that point. Also, if the patient does not receive an anesthetic level from the initial bolus plus infusion after 20 minutes, the epidural catheter will be documented as a failed catheter, and the patient will be removed from the study. The anesthesia provider will replace the epidural catheter in standard fashion if the patient requests to have it replaced.

The endpoint for our primary outcome will be the time it takes to achieve the T₁₀ level to pin prick, which should occur before 20 minutes; however, we will continue to monitor the patient throughout the 20 minute interval to determine the maximal spread of the LA (via measurement of the dermatome level by pin prick and ice), the degree of motor weakness, and if any hypotension occurs. During this time, the patient will have standard monitoring that all patients in labor receive: non-invasive BP and pulse recording and non-invasive FHR tracing. The L&D nurse, obstetricians, and anesthesiologists involved in the patient's care will deliver the same standard of care given to all patients on the L&D floor. Once the study is complete (after 20 minutes), the patient will continue to receive LA infusion through the epidural catheter throughout the remainder of labor and delivery. The anesthesia provider will continue to care for the patient throughout the patient's labor and delivery.

On average 5 to 10 patients are scheduled for induction each week. If 60% are consented for the study, then it should take approximately 3 months to enroll 45 patients.

Projected Overall Study Timeline

	Study Start-Up	Enrollment	Data Entry and Analysis	Study Write-Up
MM YYYY	08/2014			
MM YYYY		08/2014-11/2014		
MM YYYY			11/2014	12/2014

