11.0 STATISTICAL CONSIDERATIONS

The outcome Y is time to T_{10} sympathectomy. An ANOVA will be used to estimate the overall difference of the mean onset times between study groups. An estimate of onset times of 5, 6 and 7 minutes and an estimated variance of 1 min is based on the existing literature.¹² Using an alpha = 0.05, 80% power and a calculated effect size of $f = 0.82$, the total sample size sample size based on an ANOVA is N=18. Accounting for some prediction inaccuracy, we propose a target sample size of N=45, n=15 per study group.

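### A dosed patient who has some block but has not reached T10 by 20 minutes has no value the planned ANOVA of onset times can use, and the plan does not say how she is analysed

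*Combined protocol and SAP*

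**What the plan says.** Sections 4.0 and 8.0 of the combined protocol and SAP define the primary outcome as the time to a T10 level by pin prick. Section 4.0 gives the schedule: "data will then be collected 5, 10, 15, and 20 minutes after the bolus". Section 8.0 repeats it ("Then at intervals of 5, 10, 15, and 20 minutes, the investigator will document") and treats the study as complete after 20 minutes.

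On reaching T10, section 8.0 states an expectation and not a rule: "which should occur before 20 minutes; however, we will continue to monitor the patient throughout the 20 minute interval". Its only outcome-based rule at 20 minutes concerns a patient who "does not receive an anesthetic level from the initial bolus plus infusion after 20 minutes". Her catheter is "documented as a failed catheter, and the patient will be removed from the study".

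Section 11.0 gives the only planned analysis: "An ANOVA will be used to estimate the overall difference of the mean onset times between study groups". The sample size rests on "An estimate of onset times of 5, 6 and 7 minutes and an estimated variance of 1 min". No section gives a censoring rule, a substitute value, an analysis set or a missing-data rule.

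**The concern.** A patient may have a block at 20 minutes that has not risen to T10. The last reading shows only that her time exceeds 20 minutes, and an ANOVA of means cannot use that information. If she is dropped, entry into the primary comparison depends on the primary outcome. If she is given a number, that number is chosen once the data are known.

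If non-reach is more common in one arm, leaving these patients out makes that arm look faster. Bupivacaine (B) is the arm most exposed if the general epidural onset ranges in section 2.0 apply: 10-20 minutes, ending at the cut-off, against 5-15 for lidocaine (L). Losing slow B patients would shrink B-L, which works against the hypothesis that lidocaine is fastest. It would also shrink the difference between B and the mixture (BL), which works toward the hypothesis that the mixture is not significantly faster. Section 5.0 (interpretation of expected results) uses the B-BL contrast to judge whether adding lidocaine helps. A solution that often stops short of T10 would show this only in the secondary outcome of total spread.

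**Working it through.** **1. The plan's own figure.** Inputs from section 11.0: means 5, 6, 7; variance 1; alpha 0.05; 80% power. f = sqrt[((5-6)² + (6-6)² + (7-6)²)/3]/1 = 0.816. With noncentrality N·f² and 2 and N-3 degrees of freedom, power is 0.805 at N=18, so the stated N reproduces. At N=45 it is 0.9985, for times measured continuously.

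**2. Non-reach under those inputs.** For the slowest arm, 20 minutes lies (20-7)/1 = 13 SD above the mean. Slow onset past 20 minutes is effectively impossible, so the planning figures foresee no such patient.

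**3. Non-reach under slower onset (assumptions).** Normal times, with L mean 10 and B mean 15 (midpoints of the section 2.0 ranges) and BL assumed halfway at 12.5. With a = (20-μ)/σ:
- share not at T10 by 20 minutes: p = 1-Φ(a)
- mean among those who reach it: μ - σ·φ(a)/Φ(a)
- chance of at least one non-reacher among 45: 1 - Π(1-p)^15 over the three arms

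Example at SD 5:
- B: a = 1, mean 15 - 5×0.2420/0.8413 = 13.56
- BL: a = 1.5, mean 12.5 - 5×0.1295/0.9332 = 11.81
- B-BL is 1.76 instead of 2.5 (from unrounded means)

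| SD | B not at T10 | At least one of 45 | B-L (true 5.0) | B-BL (true 2.5) |
|---|---|---|---|---|
| 2.5 | 2.3% | 31% | 4.86 | 2.37 |
| 3 | 4.8% | 57% | 4.69 | 2.24 |
| 4 | 10.6% | 89% | 4.25 | 1.97 |
| 5 | 15.9% | 98% | 3.84 | 1.76 |

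SD 2.5 puts 10-20 minutes at ±2 SD and fits the range best; there the loss is small.

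**4. Power for the same cases.** Simulated with 15 per arm and times rounded up to the next 5-minute assessment.

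| SD | ANOVA, non-reachers dropped | Kruskal-Wallis, non-reachers worst rank |
|---|---|---|
| 2.5 | about 98-99% | about 98-99% |
| 4 | about 69% | about 78% |
| 5 | about 46% | about 59% |

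A rank test that also drops non-reachers gives about 66% and 43% at SD 4 and 5. The gain comes from keeping the patients, not from changing the test.

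**5. Blocks that plateau below T10 (no document input).** Suppose reachers have the same times in every arm (mean 6, SD 1) and 0%, 15% and 30% of L, BL and B never reach T10. The completers-only ANOVA finds a difference in about 4-5% of trials, and the worst-rank test in about 31-32%.

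**6. Where keeping patients costs power.** Planning figures, 5-minute grid, 15 per arm. With no non-reachers, power is about 85%.

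| Case | Worst-rank test | Non-reachers left out (ANOVA) |
|---|---|---|
| One technical failure, random arm | about 79% | about 87% |
| Three technical failures, random arms | about 62% | about 83% |
| 10% of every arm plateau below T10 | about 52% | about 82% |

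Entering 20 as a stand-in in an ANOVA gives about 60% with one technical failure in a random arm.

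**The case against.** **The failed-catheter rule may already cover her.** The opening of section 8.0 describes an adequate level as T10. Read with that, the removal rule could take her out. Read literally, it removes only a patient with no level, and she stays. A reader might infer that she definitely stays in the study; the wording does not settle it. The objection stands as a point about ambiguity, but it does not rescue the analysis. If she is removed, a randomised and dosed patient leaves because of her primary outcome; if she stays, she has no value.

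**Nothing happens under the plan's own inputs.** This is correct. Every arm also receives "the routine test dose of 3 mL of 1.5% lidocaine with 1:200,000 epinephrine" and the same infusion (section 9.0). The section 2.0 ranges are general epidural onset times, not times to T10 for these solutions. The documents therefore do not show that bias will occur or that it will favour B.

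**Removing patients with no level is not in itself biased.** A reader might infer that it is. It biases the comparison only if failure relates to the solution, which the documents neither show nor exclude. They give no criterion separating a catheter fault from a weak block. Nor can blinding be assumed to protect the decision: the recording investigator is blinded, but section 8.0 does not say who documents a failed catheter, and under section 6.0 the provider knows the drug. That is no evidence of arm-driven judgement.

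**Worst rank can lose more power than it gains.** For technical failures this stands, and it is why failed catheters should be handled separately from patients with a level below T10.

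**Conclusion.** The gap is real: the plan gives no analysable value for a dosed patient with some level who is not at T10 by 20 minutes, on either reading of the removal rule. It should be fixed. Confidence is high for the missing handling, and moderate to low for the size and direction of any bias.

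The size depends on an onset distribution and a non-reach rate that the documents do not give. The effect is nil under the planning figures, small at SD 2.5 and appreciable at SD 4-5 under the assumed means. If non-reach is equally common in all arms and unrelated to onset speed, there is no bias, but the handling would still be decided after the data are seen.

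A reader might also infer that the sample size is wrong. It is not, on this point: N=18 reproduces. The fall from 0.9985 to about 85% at N=45 comes from the 5-minute assessment grid, not from non-reachers.

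**What to change.** - In 8.0, state for analysis purposes whether the level named in the failed-catheter rule means any level or T10.
- In 8.0 and 11.0, keep every dosed patient with any level in the primary analysis. Score those not at T10 by 20 minutes as >20, and replace the ANOVA of means with a Kruskal-Wallis test that takes >20 as the worst rank. Do not enter a stand-in number in an ANOVA.
- Leave patients with no level at all out of the primary analysis and report them by arm. Pre-specify a sensitivity analysis that counts them as >20.
- Report by arm the proportion at T10 by 5, 10, 15 and 20 minutes.
- Restate power at N=45 for the chosen test on the 5-minute grid. No change in N is proposed.

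Cost: a few sentences in two sections. A rank test gives no mean difference, which the proportions at each time partly replace. Plateaus below T10 that are unrelated to the solution dilute the test, as the 10% case above shows. Catheter replacement and patient care are unaffected.

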2.0 BACKGROUND & RATIONALE

The most common and effective method for controlling labor pains is a local anesthetic infusion through a lumbar epidural.¹ To achieve adequate pain control during the first stage of labor – onset of contractions to complete cervical dilation – nerve fibers up to the T₁₀ dermatome must be anesthetized.¹ When a patient is in active labor and an epidural catheter is placed, the anesthesiologist must activate the epidural by administering LA through the epidural to promote spread of the LA in the epidural space to anesthetize the nerve fibers involved in the conduction of labor pains. The ideal LA to achieve this goal is one that would allow for the fastest onset to achieve quick pain relief with the fewest side effects. Common side effects of LA used in labor epidurals include maternal hypotension and motor blockade.³

Two commonly used LA to provide labor analgesia are bupivacaine and lidocaine. When low concentrations – 0.125% bupivacaine and 1% lidocaine – are used for labor analgesia, both of these LA can be administered safely with very little concern of major adverse effects associated with LA toxicity. However, more common side effects such as maternal hypotension requiring vasopressor therapy and motor blockade can often occur.³

Though both are amide LA, bupivacaine and lidocaine display different properties that give each an advantage in certain situations. Lidocaine's onset of action is faster than that of bupivacaine's (5-15 vs. 10-20 minutes for epidural injection).¹ Whereas bupivacaine has a longer duration of action (180-300 vs. 60-180 minutes).¹ Through a sympathetically mediated veno- and vaso-dilation, both LA commonly cause hypotension. Although the time to develop hypotension was not noted, several studies have noted a higher incidence of hypotension with the administration of epidural lidocaine vs. bupivacaine.^{2,4}

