Given that there is limited and conflicting evidence for the usefulness of the bupivacaine and lidocaine mixture especially as it relates to labor epidural activation, we hope to readdress these questions in an effort to determine whether or not the LA combination offers any distinct advantage over the individual LA. In contrast to Sinatra et al's study, we intend to determine the time it takes to achieve an adequate level (T₁₀) for labor analgesia, the total spread of local anesthetic (both caudal and rostral), and the time it takes to develop hypotension – not just the overall incidence – as these factors will be important in determining the most optimal LA solution to activate a labor epidural. We will also reevaluate the degree of motor block, as patients in Sinatra's study received a much higher concentration of bupivacaine (0.5%) than we use for epidural activation (0.125%). With the results of our study, we hope to recommend a LA solution that will allow for the fastest pain relief in the laboring mother with the fewest side effects.

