We hypothesize that lidocaine will achieve a T₁₀ level the fastest when compared to bupivacaine and bupivacaine plus lidocaine. The bupivacaine plus lidocaine solution's onset of action will not be significantly faster when compared to bupivacaine. Given the concentration of the bupivacaine, less hypotension and motor block will be present when compared to the lidocaine and bupivacaine plus lidocaine. The bupivacaine plus lidocaine will offer no increased benefit of having a faster onset with less hypotension or motor blockade than either LA solution alone.

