5.0 INTERPRETATION OF EXPECTED RESULTS

06_18_2014

If we see a significant decrease in time to achieve a T₁₀ dermatome level with the bupivacaine and lidocaine mixture compared to the bupivacaine only solution, then that would imply that the addition of the lidocaine did speed up the onset of action of the LA solution we used to activate the epidural. We would also need to account for each LA solution's side effect profile. By measuring the incidence of hypotension and degree of motor blockade, we will be able to determine if one solution's side effect profile is more favorable. By determining the advantages vs. disadvantages of each solution, we would be able to recommend the most ideal LA solution of those studied as the solution best suited for activation of labor epidurals.

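### A 20-minute stop cannot be assumed to capture maximal spread, peak motor block or overall hypotension, and any shortfall falls more on the slower-onset arm

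*Combined protocol and SAP*

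**What the plan says.** Section 4.0 fixes the reading schedule: starting from the bolus, "data will then be collected 5, 10, 15, and 20 minutes after the bolus". Section 8.0 gives the purpose of the full window: "we will continue to monitor the patient throughout the 20 minute interval to determine the maximal spread of the LA", along with motor weakness and any hypotension. It then ends study observation: "Once the study is complete (after 20 minutes"), the patient simply continues on the infusion. The Summary and Section 4.0 call the spread outcome *total*, and Section 8.0 uses both *total* and *maximal*. No outcome is labelled as applying to the first 20 minutes only, and nothing checks whether the block has stopped rising.

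On onset, Section 2.0 states: "Lidocaine's onset of action is faster than that of bupivacaine's (5-15 vs. 10-20 minutes for epidural injection"). Section 11.0 plans on mean times of 5, 6 and 7 minutes with variance 1, without assigning them to arms. Section 8.0 expects T10 to be reached before 20 minutes.

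On use of the data, Section 4.0 predicts: "Given the concentration of the bupivacaine, less hypotension and motor block will be present when compared to the lidocaine and bupivacaine plus lidocaine". The section on interpretation of expected results says: "By measuring the incidence of hypotension and degree of motor blockade, we will be able to determine if one solution's side effect profile is more" (the closing word there is favorable), and goes on to a recommended solution. Section 2.0 also makes the timing of hypotension an aim ("the time it takes to develop hypotension – not just the overall incidence") and says of earlier work: "Although the time to develop hypotension was not noted".

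**The concern.** A maximum or a cumulative incidence read at a fixed clock time is complete only if the process has finished by then. If one drug starts later, the same clock leaves it less time to show its peak level, its peak motor score or a fall in blood pressure. Lower recorded motor block or hypotension with bupivacaine could then partly reflect later onset, yet the plan would read it as a better side-effect profile and carry it into the recommendation. Since the protocol says that the time to hypotension is not known from earlier studies, it offers no ground for taking 20 minutes as long enough.

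**Working it through.** **The plan's own figure.** The only calculated figure is the Section 11.0 sample size. With means 5, 6, 7 and SD 1, f = √(2/3)/1 = 0.816. A one-way ANOVA with three groups and alpha 0.05 has power 0.805 at N = 18 and 0.70 at N = 15, so N = 18 reproduces. It concerns time to T10 and does not depend on this point.

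**Time observed after onset** (20 minutes minus onset):
- Section 2.0 ranges: lidocaine 20 − 15 = 5 to 20 − 5 = 15 minutes; bupivacaine 20 − 20 = 0 to 20 − 10 = 10 minutes.
- Section 11.0 times of 5, 6, 7: 15, 14, 13 minutes.

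If onset were uniform over 10-20 minutes (assumed), half of bupivacaine patients would have onset at 15-20 minutes. Their first recorded level would be the 20-minute reading, which would also stand as their maximum. No lidocaine patient would be in that position under 5-15 minutes.

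**Illustration for an event such as hypotension.** Assumptions not in the documents: uniform onset over the Section 2.0 ranges; an exponential lag from onset to event with mean m, the same in both arms; the same true eventual incidence, 40%, in both arms. With time left after onset running from a to b (b − a = 10), the share of events seen by 20 minutes is

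1 − (m/10)(e^(−a/m) − e^(−b/m)),

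with a = 5, b = 15 for lidocaine (L) and a = 0, b = 10 for bupivacaine (B). For m = 5: L = 1 − 0.5(0.368 − 0.050) = 0.841; B = 1 − 0.5(1 − 0.135) = 0.568.

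For comparison, if Section 11.0's 5 minutes is lidocaine and 7 is bupivacaine (also an assumption), the shares are 1 − e^(−15/m) and 1 − e^(−13/m).

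| Mean lag m (min) | L, B seen (Section 2.0 ranges) | Ratio | L, B seen (5 and 7 min) | Ratio |
|---|---|---|---|---|
| 2 | 0.98, 0.80 | 1.23 | 0.999, 0.998 | 1.00 |
| 5 | 0.841, 0.568 | 1.48 | 0.950, 0.926 | 1.03 |
| 10 | 0.617, 0.368 | 1.68 | 0.777, 0.727 | 1.07 |
| 20 | 0.387, 0.213 | 1.82 | 0.528, 0.478 | 1.10 |

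With 40% true incidence in both arms, the Section 2.0 ranges would record about 34% vs 23% (m = 5), 25% vs 15% (m = 10) and 15% vs 9% (m = 20).

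**In patients.** With 15 per arm, 40% is 6 eventual events per arm. The spurious gap is 6 × (0.841 − 0.568) = 1.6 patients at m = 5, 6 × (0.617 − 0.368) = 1.5 at m = 10 and 6 × (0.387 − 0.213) = 1.0 at m = 20. Under 5 and 7 minutes it is at most 6 × (0.528 − 0.478) = 0.3.

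The combination arm is not modelled, because Section 2.0 gives no onset range for it.

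**What later data would measure.** Section 9.0 starts 0.1% bupivacaine (1 mg/mL) at 10 mL/hr in all arms after the bolus. That is 10 × 20/60 = 3.3 mg by 20 minutes and 10 mg by 60 minutes. The boluses contain 10 mL × 1.25 mg/mL = 12.5 mg bupivacaine (B), 6.25 mg (combination) and none (L). By 60 minutes every arm has received a further 10/12.5 = 80% of the B bolus.

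**The case against.** A common fixed window is a legitimate comparison for epidural activation, and the reading times are stated openly. That stands: outcomes defined as within 20 minutes would be valid. The difficulty is calling them maximal, total or overall.

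The Section 2.0 range is general and does not define onset, whereas Section 11.0 gives planning values for this trial's own endpoint, and Section 8.0 expects T10 before 20 minutes. On those figures the tilt is slight. This stands as a limit on size. It does not dispose of the point, because the two sections disagree and reaching T10 is not the same as reaching peak level or the end of hypotension risk.

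Every patient also receives a lidocaine test dose before time zero (3 mL of 1.5%, or 45 mg), so no bupivacaine-arm block is purely bupivacaine. Section 2.0 cites an epidural study with no difference in time to T4 across lidocaine, bupivacaine and the combination. Both are reasons not to take the illustrative ratios as estimates.

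A reader might infer that truncated spread also favours the hypothesis. It does not: the hypothesis in Section 4.0 makes no prediction about spread, and since Section 3.0 seeks the best coverage, under-recorded spread would count against bupivacaine. A reader might also infer that counting hypotension to 60 minutes would remove the problem. The infusion arithmetic shows that such a count answers a different question. It would also rest on routine records rather than the blinded investigator's timed readings, at a frequency the documents do not state.

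**Conclusion.** The point holds in a limited form. On the protocol's own onset ranges, 20 minutes cannot be assumed to capture the maximum level, the peak motor score or the overall incidence of hypotension, and any shortfall is larger in the slower-onset arm. For motor block and hypotension the direction favours the stated hypothesis.

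The size cannot be derived from the documents. It could be material under the Section 2.0 ranges (about 1 to 1.6 patients of 15 in the illustration) and is small under the Section 11.0 times if 5 minutes is lidocaine and 7 is bupivacaine. Both results rest on an assumed lag, and the patient counts also on an assumed incidence. A reader might take ratios of 1.5 to 1.8 as the expected bias; the documents do not support that.

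Nor do they support extending the point to the trial's main result. The primary outcome and the sample size are not affected; only the secondary outcomes and the side-effect part of the recommendation are.

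**What to change.** 1. In the Summary and Sections 4.0 and 8.0, define spread, motor block and hypotension as observed within 20 minutes of the bolus, and drop *maximal* and *total*. In the section on interpretation of expected results, limit the side-effect conclusion to the first 20 minutes.
2. Report by arm how many patients were still gaining dermatomes or motor score between the 15- and 20-minute readings, and do not call the 20-minute value a maximum for them.
3. Reconcile the onset ranges in Section 2.0 with the planning times in Section 11.0: say what onset means in each and which planning time belongs to which arm.
4. Optionally, as a descriptive sensitivity analysis only, abstract later blood pressure and vasopressor use from the routine record, stating that it reflects bolus plus common infusion and was not recorded by the blinded investigator.

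Items 1 to 3 need only wording and a tabulation of data already planned: no extra patients, readings or staff. Item 4 costs chart abstraction and yields figures increasingly shaped by the infusion.
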